## Part 2: Bayesian Optimal Phase 2 Design (BOP2)

### Justification for response rates that will be considered futile

Based on previous publications and scientific review (in the table below), the response rate of 20-35% for R/R MM and 25-45% for R/R DLBCL has been used in the SET-101 protocol. For R/R MM, an objective response rate of 20-35% has been reported for monotherapies ([Richardson, 2009](#); [Siegel, 2012](#); [Lonial, 2020](#)). For R/R DLBCL, an objective response rate of 25-45% has been reported for monotherapies ([Mondello, 2016](#); [Davids, 2017](#); [Kalakonda, 2020](#)) that are not CAR-T or bi-specifics and are not known to cause cytokine release syndromes.

Study	ORR	Number of Subjects
R/R MM		
Carfilzomib (Siegel et al 2012)	23.7% (95% CI, 18.7-29.4)	257
Lenalidomide (Richardson et al 2009)	26% (95% CI, 25.7-26.5)	222
Belantamab mafodotin (Lonial et al, 2020)	34% (97.5% CI, 23.9-46.0)	99

Study	ORR	Number of Subjects
R/R DLBCL		
Venetoclax (Davids et al 2017)	22%	41
Selinexor (Kalakonda et al 2020)	28% (95% CI, 20.7-37.0)	127
Lenalidomide (Mondello et al 2016)	37%	123

Using meta-analysis with fixed effect model for 3 MM studies, the lower 95% CI is 22.5%. Therefore, 20% response rate was selected that will be considered futile. Using meta-analysis with fixed effect model for 3 DLBCL studies, the lower 95% CI is 25.6%. Therefore, 25% response rate was selected that will be considered futile in this proof of concept Phase 1b dose expansion part of the study.

In the dose expansion part of the study, the following cohorts of subjects will receive EZM0414 monotherapy at MTD orally once daily (QD) in 28-day cycles:

- Cohort 1: R/R MM with t(4;14) translocation
- Cohort 2: R/R MM without t(4;14) translocation
- Cohort 3: R/R DLBCL

Subjects treated at MTD in Phase 1 dose escalation part of the study will continue to receive the treatment beyond cycle 1 (be rolled over to this dose expansion part) until disease progression, occurrence of unacceptable toxicity, or withdrawal of consent, or need for treatment prohibited on this study.

Bayesian optimal phase 2 design (Yuan, 2016; Zhou, 2017) will be applied to the Phase 1b dose expansion part to discover efficacy signals. Twenty (20) subjects/cohort are planned to be enrolled and 3 looks will be performed when the data of 10, 15 and 20 subjects have been available. The cohort will be terminated if deemed futile.

### For R/R MM

There will be 2 cohorts of R/R MM subjects enrolled in this part of the study. They are with and without t(4;14), respectively. Relapsed/refractory MM subjects treated at MTD in the dose escalation part will be rolled over to either Cohort-1 R/R MM with t(4;14) or Cohort-2 R/R MM without t(4;14) depending on their translocation status.

For either of these 2 cohorts let  $n_M$  denote the interim sample size and  $N_M$  denote the maximum sample size. Also let  $p_{Meff}$  denote the objective response rate (ORR) and define the null hypothesis.  $H_0: p_{Meff} \leq 0.2$ , under which the treatment is deemed as unacceptable. We will stop enrolling subjects and claim that the treatment is futile if

$$Pr(p_{Meff} > 0.2 | data) < \lambda_M \left( \frac{n_M}{N_M} \right)^{\alpha_M}$$

where  $\lambda_M=0.84$  and  $\alpha_M=1$  are design parameters optimized to maximize power under the alternative hypothesis  $H_1: p_{M_{eff}} = 0.35$ , (ie, the probability of correctly claiming that the treatment is acceptable under  $H_1$ ), while controlling the type I error rate (ie, the probability of incorrectly claiming that the treatment is acceptable under  $H_0$ ) at 0.084. This optimization is performed assuming a vague prior Beta (0.2, 0.8) for  $p_{M_{eff}}$ . The above decision rule leads to the following stopping boundaries and yields a statistical power of 0.571 under  $H_1$ :

**Table 16: Optimized Stopping Boundaries for R/R MM Cohort**

Sample size for interim looks	Stop if # Response $\leq$
10	1
15	3
20	6

ORR = Objective response rate; R/R = Relapsed/refractory; MM = Multiple myeloma.  
 $H_0$ : ORR (Futile)=0.2;  $H_1$ : ORR (Promising)=0.35; Type I Error Rate=0.1

Based on [Table 16](#), futility assessments will be conducted for each R/R MM cohort when response assessment data become available (ie, minimum 5 cycles or if all subjects progressed) in the first 10 enrolled subjects, and again in the first 15 enrolled subjects. Enrolment will not cease during the assessment periods. When the response assessment data are available for the total number of 20 subjects, we reject the null hypothesis for the cohort and conclude that the treatment is promising (go) if the number of responses is more than 6 ( $>6$ ); otherwise, we conclude that the treatment is futile (no-go). The go/no-go criteria in [Table 16](#) are non-binding.

### For R/R DLBCL

One cohort of 20 subjects with R/R DLBCL will be enrolled in the dose expansion part of the study following BOP2 design. The subjects with R/R DLBCL treated at MTD in the dose escalation part of the study will be rolled over to this dose expansion part until disease progression, occurrence of unacceptable toxicity or withdrawal of consent occurred.

Let  $n_D$  denote the interim sample size and  $N_D$  denote the maximum sample size for this cohort. Also let  $p_{D_{eff}}$  denote the ORR and define the null hypothesis  $H_0: p_{D_{eff}} \leq 0.25$ , under which the treatment is deemed as futile. We will stop enrolling subjects and claim that the treatment is unacceptable if

$$Pr(p_{D_{eff}} > 0.25 | data) < \lambda_D \left( \frac{n_D}{N_D} \right)^{\alpha_D},$$

where  $\lambda_D=0.82$  and  $\alpha_D=0.51$  are design parameters optimized to maximize power under the alternative hypothesis  $H_1: p_{D_{eff}} = 0.4$ , (ie, the probability of correctly claiming that the treatment is acceptable under  $H_1$ ), while controlling the type I error rate (ie, the probability of incorrectly claiming that the treatment is acceptable under  $H_0$ ) at 0.093. This optimization is performed assuming a vague prior Beta (0.25, 0.75) for  $p_{D_{eff}}$ . The above decision rule leads to the following stopping boundaries and yields a statistical power of 0.555 under  $H_1$ :

**Table 17: Optimized Stopping Boundaries for R/R DLBCL Cohort**

Sample size for interim looks	Stop if # Response ≤
10	2
15	4
20	7

ORR = Objective response rate; R/R = Relapsed/refractory; DLBCL = diffuse large B cell lymphoma  
 $H_0$ : ORR (Futile)=0.25;  $H_1$ : ORR (Promising)=0.4; Type I Error Rate=0.1

Based on [Table 17](#), futility assessments will be conducted when response assessment data become available (ie, minimum 5 cycles or if all subjects progressed) in the first 10 enrolled subjects, and again in the first 15 enrolled subjects. Enrolment will not cease during the assessment periods. When the total number of subjects reaches the maximum sample size of 20, we reject the null hypothesis and conclude that the treatment is acceptable (go) if the number of responses is more than 7 ( $>7$ ); otherwise, we conclude that the treatment is unacceptable (no-go). The go/no-go criteria in [Table 17](#) are non-binding.

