#### 7.5.6. Determination of Sample Size and Criteria for Early Stopping Due to Futility

This is a FIH study. The objective of this study is to evaluate the safety, tolerability, and PK of EZM0414 in order to determine MTD in Phase 1 part, and safety, tolerability, PK, and efficacy to determine RP2D in Phase 1b part.

This is an open-label study and there will be no randomization. Subjects will be enrolled based on their conditions.

The sample size of Phase 1 part is determined based on number of doses to be tested using BOIN design and there is no formal sample size estimation for the Phase 1b part of the study.

The study will enroll approximately 96 subjects, of which up to 36 subjects will be enrolled in Phase 1 dose escalation part and 60 subjects (20 subjects/cohorts) will be enrolled in Phase 1b dose expansion part. There will be 6 dose levels (starting at 100 mg, then 200 mg, 300 mg, 400 mg, 600 mg, and 900 mg) as well as an optional step-down dose level of 75 mg (if needed) to be tested in Phase 1 dose escalation part to determine MTD, and additional daily dose levels and/or dosing schedules (including BID regimen) may be studied based on clinical and pharmacokinetic data obtained during this study. The sample size will therefore be adjusted accordingly. There will be 3 cohorts for the dose expansion part: 20 R/R MM subjects with t(4;14), 20 R/R MM subjects without t(4;14) and 20 R/R DLBCL subjects.

The subjects who are treated at MTD in Phase 1 dose escalation part and do not experience any DLT will continue to receive the treatment beyond cycle 1 (be rolled over to the dose expansion part) until disease progression, occurrence of unacceptable toxicity, or withdrawal of consent, or need for treatment prohibited on this study.

There will be 3 looks performed in Phase 1b part when the data of 10, 15, and 20 subjects of a cohort have been available. The cohort will be terminated earlier if deemed futile by SRC and the study team.

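### The stated type I errors of 0.084 (MM) and 0.093 (DLBCL) assume the futility stops at 10 and 15 are obeyed, yet the plan calls them non-binding; with every stop overridden they are 0.087 and 0.102

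*Protocol*

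**What the plan says.** Protocol Section 14.1 defines the expansion design cohort by cohort, with looks at 10, 15 and 20 subjects.

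- **The rule is worded as mandatory.** For MM: "We will stop enrolling subjects and claim that the treatment is futile if" the posterior probability falls below the cut-off. For DLBCL: "We will stop enrolling subjects and claim that the treatment is unacceptable if" the corresponding condition is met.
- **Error and power are attached to that rule.** MM: type I error 0.084 at a response rate of 0.20, power 0.571 at 0.35. DLBCL: 0.093 at 0.25, power 0.555 at 0.40. The notes under Tables 16 and 17 each print "Type I Error Rate=0.1".
- **The boundaries.** Table 16 (MM) stops at 1 or fewer of 10, 3 or fewer of 15, and 6 or fewer of 20. Table 17 (DLBCL) stops at 2, 4 and 7 or fewer. At 20 subjects the cohort is a go with more than 6 (MM) or more than 7 (DLBCL) responses.
- **The status of the boundaries.** The text under each table then says "The go/no-go criteria in [Table 16](#) are non-binding" and "The go/no-go criteria in [Table 17](#) are non-binding".
- **Who decides.** Section 7.5.6: "The cohort will be terminated earlier if deemed futile by SRC and the study team".

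No error rate is given for a cohort that crosses an interim stop and continues.

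**The concern.** A futility stop removes some cohorts that would otherwise have reached the final go threshold by chance. A type I error computed with the stops in force takes credit for that removal. If the stops need not be followed, the credit is not assured. The figure that holds whatever is decided at the interim looks is then the one computed as if those looks did not exist. Section 14.1 pairs the lower figure with wording that permits overrides.

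An override is a foreseeable path. Accrual continues while a look is assessed, and each look waits for at least 5 cycles of response data (5 × 28 = 140 days) unless all subjects have progressed. The accrual rate is not given, but with fast accrual a cohort could be full before its 10-subject result is known. Suppose a DLBCL cohort then has 2 of 10 at the first look and 8 of 20 at the end. The plan does not say whether that is a go, and the stated error depends on the answer.

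At stake is whether the operating characteristics claimed for the design are the ones it delivers.

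**Working it through.** **Inputs** (Protocol Section 14.1). MM: λ = 0.84, α = 1, prior Beta(0.2, 0.8), null 0.20, alternative 0.35. DLBCL: λ = 0.82, α = 0.51, prior Beta(0.25, 0.75), null 0.25, alternative 0.40. Looks at 10, 15 and 20.

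**Step 1: boundaries.** With x responses in n and prior Beta(a, b), stop if Pr(p > p0 | x) < λ(n/20)^α, where p | x ~ Beta(a + x, b + n − x).

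| Cohort | n | Cut-off | Largest x that stops (posterior) | Next x (posterior) |
|---|---|---|---|---|
| MM | 10 | 0.84 × 0.5 = 0.42 | 1 (0.150) | 2 (0.439) |
| MM | 15 | 0.84 × 0.75 = 0.63 | 3 (0.450) | 4 (0.692) |
| MM | 20 | 0.84 | 6 (0.831) | 7 (0.928) |
| DLBCL | 10 | 0.82 × 0.5^0.51 = 0.576 | 2 (0.310) | 3 (0.596) |
| DLBCL | 15 | 0.82 × 0.75^0.51 = 0.708 | 4 (0.521) | 5 (0.735) |
| DLBCL | 20 | 0.82 | 7 (0.8194) | 8 (0.918) |

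Tables 16 and 17 are reproduced.

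**Step 2: the stated errors, stops obeyed.** P(go) = P(X10 > r1, X15 > r2, X20 > r3), by exact binomial recursion over 10 + 5 + 5 subjects. Under the null, the probabilities of stopping at the three looks are:

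- MM: 0.3758 + 0.2886 + 0.2520 = 0.9164, so P(go) = 0.0836.
- DLBCL: 0.5256 + 0.1930 + 0.1879 = 0.9066 (summed before rounding), so P(go) = 0.0934.

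Under the alternative, P(go) is 0.5715 and 0.5550. All four match the protocol's 0.084, 0.093, 0.571 and 0.555. A simulation of 2 million cohorts per scenario agrees (0.0835, 0.0933, 0.5712, 0.5555).

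**Step 3: stops overridden, final threshold kept.** If neither interim stop is applied, P(go) = P(X20 > r3). For MM, P(X ≥ 7 | 20, 0.20) = 0.0867. For DLBCL, P(X ≥ 8 | 20, 0.25) = 0.1018.

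| Interim stops obeyed | MM error | MM power | DLBCL error | DLBCL power |
|---|---|---|---|---|
| Both | 0.0836 | 0.571 | 0.0934 | 0.555 |
| Only at 10 | 0.0849 | 0.576 | 0.0956 | 0.562 |
| Only at 15 | 0.0849 | 0.577 | 0.0981 | 0.572 |
| Neither | 0.0867 | 0.583 | 0.1018 | 0.584 |

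The increase is the null probability of crossing an interim stop and still reaching the final threshold: 0.08669 − 0.08358 = 0.0031 (MM) and 0.10181 − 0.09343 = 0.0084 (DLBCL).

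**Step 4: occasional overrides (assumption).** If each crossed DLBCL stop is overridden independently with probability q, the error is 0.0952 at q = 0.25, 0.0972 at 0.5 and 0.0994 at 0.75. It passes 0.10 between q = 0.81 (0.09997) and q = 0.82 (0.10007).

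**Step 5: the 20-subject row.** The non-binding sentence covers the whole table. If that row can also be set aside, 0.087 and 0.102 are no longer maxima. As an illustration, with the interim stops ignored, calling go on one response fewer gives P(X ≥ 6 | 20, 0.20) = 0.196 for MM and P(X ≥ 7 | 20, 0.25) = 0.214 for DLBCL.

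**The case against.** The printed figures are correct for the rule they describe, so this is a gap in reporting rather than a miscalculation. That is right: no sum in Section 14.1 is wrong. What fails is the claim of control once the rule is made optional.

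The size is also modest. The maxima need every crossed stop to be overridden. DLBCL stays below 0.10 until roughly four in five are ignored, and power rises rather than falls. The note under Table 17 prints one decimal, to which 0.1018 still rounds. The expansion is a proof-of-concept signal search without formal sample size estimation (Section 7.5.6) or multiplicity adjustment (Section 14.9). The SAP covers dose escalation only, after early termination (SAP Section 1), with interim, Phase 1b and efficacy analyses marked not applicable. All of this stands and limits the priority of the point.

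The wording can be read more kindly. Go and no-go are named only at the 20-subject decision, so the non-binding sentence might concern development decisions rather than the test. Section 7.5.6 might only name who applies the boundaries, and the synopsis does speak of pre-specified ones. These readings are possible, but none says that a cohort which crossed a stop is barred from go. If the sentence concerns the final row instead, the cap on the error becomes less certain, not more.

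That non-binding futility is common practice does not answer the point. Under that practice the error to report is the one that ignores the stops.

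**Conclusion.** The concern holds. The protocol's 0.084 and 0.093 are the lowest values of a range that its own non-binding wording opens. With the 20-subject thresholds kept, the ranges are 0.0836 to 0.0867 (MM) and 0.0934 to 0.1018 (DLBCL). MM stays below 0.1 throughout. DLBCL exceeds it by 0.0018 in the extreme case only. Power is at least the stated 0.571 and 0.555.

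These ranges assume exact binomial responses, looks at exactly 10, 15 and 20, and a final threshold that is always applied. If the final row is non-binding as well, no type I error is defined for the go decision.

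The practical effect is small, and no result is affected because no expansion cohort will be tested. The point is the accuracy of the stated operating characteristics, and it matters wherever they are reported or the design is reused.

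**What to change.** Choose one of two wordings for Section 14.1.

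- **(a) Interim stops binding for the conclusion.** State that a cohort meeting a stop boundary at 10 or 15 may continue but cannot be declared go. This preserves 0.084 and 0.093. It also gives up much of the purpose of a non-binding stop.
- **(b) Interim stops non-binding.** State that the looks at 10 and 15 are non-binding and the 20-subject threshold is binding. Report maximum type I errors of 0.087 (MM) and 0.102 (DLBCL), and correct the Table 17 note to match. Keep power as at least 0.571 and 0.555, giving 0.583 and 0.584 only as the values when every stop is overridden.

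Option (b) is closer to the plan's apparent intent. In either case, bring the mandatory wording in the MM and DLBCL subsections and the sentence in Section 7.5.6 into line with the choice.

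The core change is one sentence for (a), or one sentence, two restated error rates and one table note for (b). Neither changes the sample size or the boundaries.

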## 14.2. General Consideration for Statistical Analysis

This section is a summary of the planned statistical analyses of the most important endpoints including safety, PK, primary, and key secondary efficacy endpoints. A statistical analysis plan (SAP) will be finalized prior to final database lock. Should the SAP and the protocol be inconsistent with respect to any further planned analyses, the language of the SAP is governing.

In general, the data from Phase 1 dose escalation part and Phase 1b dose expansion part will be analyzed separately except the efficacy data from the subjects who receive the study drug at MTD in dose escalation part and are rolled over to the dose expansion part. Their efficacy data in Phase 1 part will be integrated in Phase 1b efficacy data analysis unless otherwise specified.

All tests of treatment effects will be conducted at a 2-sided alpha level of 0.05, unless otherwise stated. All tests of interactions will be conducted at a 2-sided alpha level of 0.1, and all confidence intervals (CIs) will be given at a 2-sided 95% level, unless otherwise stated.

## 14.3. Analysis Populations

**Safety Population:** Safety analyses will be composed of all subjects who receive at least 1 dose of the study drug in Phase 1 (dose escalation part) or Phase 1b (dose expansion part).

**Dose-limiting toxicity (DLT) Evaluable Population:** The DLT evaluable population will consist of dose escalation dose level subjects in the Safety Population who received at least 80% of planned study treatment during cycle 1.

**Intent-to-Treat (ITT) Population (Phase 1b Dose Expansion Portion):** The ITT Population is defined as all subjects enrolled in corresponding cohorts of Phase 1b part, regardless of their adherence with the entry criteria, the treatment they actually received, and subsequent withdrawal from treatment or deviation from the protocol. The ITT Population includes the subjects who received the study treatment at MTD in Phase 1, dose escalation part and are rolled over to the corresponding cohorts of the Phase 1b, dose expansion part.

**PK Analysis Population:** will include all subjects in the Safety Analysis population who have sufficient post-dose blood sample collected to allow estimation of the PK parameters.

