**Investigational product, dosage, and mode of administration:**

Ezm0414 will be administered orally once daily in continuous 28-day cycles. In dose escalation part, patient will not receive Ezm0414 on Cycle 1 Day 2 and on Cycle 1 Day 3, all other days will follow daily dosing in cycle 1. Each subject will receive Ezm0414 according to the dose level they are enrolled in. Intra-patient dose escalation will not be permitted. During the dose expansion part, subjects in cohorts 1-3 will receive Ezm0414 at the MTD orally once daily. Ezm0414 will be administered at approximately the same time once daily and without food, (no food two hours prior and one hour after Ezm0414 dose, water is permitted without restrictions).

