## **7.5. Dose Adjustment Criteria**

### **7.5.1. Dose Limiting Toxicities**

Any adverse event (AE) which meets the criteria of a DLT as assessed by the Investigator and warrants action as per [Table 3](#), will be reviewed by the Safety Review Committee (SRC). No intra-patient dose reduction will be permitted in Cycle 1 of dose escalation. For subjects who require a dose interruption due to a DLT during cycle 1, the treatment will be restarted once the toxicity resolves to Grade  $\leq 1$  or baseline. However, an interruption in the administration of EJM0414, for more than 14 days will be discussed with the Sponsor's or Designee Medical

Monitor before treatment can be resumed. The DLT evaluable subjects will consist of dose escalation dose level subjects who received at least 80% of planned study treatment during cycle 1. If a subject is non evaluable, this subject will be replaced by a new subject.

Safety assessments will be performed throughout the study and at each visit. DLT period is 28 days of cycle 1 of the dose escalation part. AEs that are clearly and incontrovertibly due to the underlying disease or extraneous causes will not be considered as DLTs. All of the AEs of specified grades as listed in Table 3 will be classified as DLTs. Events will be assessed as DLTs according to the Common Terminology Criteria for Adverse Events (CTCAE 5.0), as shown in [Table 3 \(Appendix 5\)](#). When a subject is assessed to be experiencing a DLT, study treatment will be interrupted and DLTs will be managed by concomitant medication (as appropriate), treatment discontinuation, or a combination of these. All dose escalation decisions will be made by the SRC and Sponsor upon review of all available data. Determination of the MTD will be informed by all available data, including the overall tolerability of EZM0414.

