**Table 3: Dose Limiting Toxicities**

Toxicity Category	Dose-Limiting Toxicity/CTCAE (version 5.0) Grade
Hematological toxicity	
 
Grade 4 neutropenia lasting more than 5 days
 
Grade 3 febrile neutropenia (ANC <math><1.0 \times 10^9/L</math> fever <math>\geq 38.4^{\circ}\text{C}</math> or <math>\geq 38^{\circ}\text{C}</math> for 1 hour)
 
Grade 3 thrombocytopenia with clinically significant bleeding
 
Grade 4 thrombocytopenia
 
Grade 4 Anemia unexplained by underlying disease
 

Other non-hematological toxicity	
 
Any other non-hematologic toxicity <math>\geq 3</math> except: 
 
Alopecia
 
Grade 3 nausea/vomiting or diarrhea for less than 3 days with adequate antiemetic and other supportive care
 
Grade 3 fatigue for less than one week
 
Grade 3 or higher isolated electrolyte abnormalities that last up to 3 days, are not clinically complicated, and resolve spontaneously, or respond to conventional medical interventions
 
Grade 3 or higher amylase or lipase elevation that is not associated with symptoms or clinical manifestations of pancreatitis
 
Grade 3 tumor lysis syndrome (TLS) that lasts up to 3 days, is not clinically complicated, and resolves spontaneously, or responds to conventional medical interventions.
 
 
 
Any patient meeting Hy's Law Criteria without alternate explanation, concurrent values of: 
 
ALT or AST elevation of <math>>3\times\text{ULN}</math>, and
 
TBL elevation of <math>>2\times\text{ULN}</math>, and
 
Absence of initial findings of cholestasis (ie, absence of elevation of ALP to <math>>2\times\text{ULN}</math>)
 
 
 

AE = adverse event; ALP = alkaline phosphatase; ALT = alanine aminotransferase; AST = aspartate aminotransferase; CTCAE = Common Terminology Criteria for Adverse Events; ECOG = Eastern Cooperative Oncology Group (ECOG); TBL = total bilirubin; ULN = upper limit of normal

*Note:* ALT is also referred to as serum glutamic pyruvic transaminase (SGPT); AST is also referred to as serum glutamic oxaloacetic transaminase (SGOT)

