**Table 14: Total Daily Dose and Respective Dose Level**

Dose Level	Total Daily Dose (mg)
-1 (optional)	75
1	100
2	200
3	300
4	400
5	600
6	900

Additional daily dose levels and/or dosing schedules (including BID regimen) may be studied based on clinical and pharmacokinetic data obtained during this study.

Bayesian optimal interval design ([Liu, 2015; Yuan, 2016; Zhou, 2017](#)) will be used for this dose escalation part. Similar numbers of subjects with R/R MM or R/R DLBCL will be enrolled to determine MTD. The target toxicity rate ( $\varrho_T$ ) for the MTD is set at **0.25** for both R/R MM and R/R DLBCL. The maximum number of subjects for determination of MTD is 9. A total of 6 dose levels ( $j = 6$ , ie, starting at 100 mg, then 200 mg, 300 mg, 400 mg, 600 mg, and 900 mg) as well as an optional step-down dose level of 75 mg will be investigated. We will enroll and treat subjects in groups of at least 3, and up to 36 subjects will be enrolled in this dose-escalation part of the study in order to evaluate at least 9 subjects for MTD. Dose limiting toxicities are defined in Section [7.5.1](#), and only those DLTs that occur within the first cycle will be used for safety assessment. The BOIN design uses the following rules, optimized to minimize the probability of incorrect dose assignment, to guide dose escalation/de-escalation:

- if the observed DLT rate at the current dose is  $\leq 0.197$ , escalate the dose to the next higher dose level;
- if the observed DLT rate at the current dose is  $\geq 0.298$ , de-escalate the dose to the next lower dose level;

- otherwise, stay at the current dose.

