**Table 15: Dose Escalation/de-escalation Rule for the BOIN Design**

Target Toxicity Rate	$\Pr(p_j > \text{targettoxicity rate}   \text{data})$	Actions	The number of evaluable patients at the current dose								
			1	2	3	4	5	6	7	8	9
0.25	0.8	Escalate if # of DLT $\leq$	0	0	0	0	0	1	1	1	1
		De-escalate if # of DLT $\geq$	1	1	1	2	2	2	3	3	3
		Eliminate if # of DLT $\geq$	NA	NA	2	2	2	3	3	3	4

BOIN = Bayesian Optimal Interval Design; DLT = Dose Limiting Toxicity; NA = Not Applicable

\* When none of the actions (ie, escalate, de-escalate, or eliminate) is triggered, stay at the current dose for treating the next group of subjects. Note that “# of DLT” is the number of subjects with at least 1 DLT, and “NA” means that a dose cannot be eliminated before treating 3 evaluable subjects.

Maximum tolerated dose will be determined based on isotonic regression as specified in Liu and Yuan (2015). When the isotonic estimate of toxicity rate  $\tilde{p}_j^*$  is closest to pre-set target DLT rate ( $\varphi_T=0.25$  for this study). If there are ties for  $\tilde{p}_j^*$  the higher dose with  $\tilde{p}_j^* <$  the target toxicity rate will be selected as MTD. Alternatively, the lower dose with  $\tilde{p}_j^* > \varphi_T$  will be selected.

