##### Dose-Limiting Toxicity (DLT) Evaluable Population

The DLT evaluable population is consist of dose escalation dose level participants in the Safety Population who received at least 80% of planned study treatment during cycle 1. Participants will be analysed according to the assigned dose level for the respective dose escalation cohort.

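### A subject becomes DLT-evaluable on doses taken (21 of 26, Day 23 at the earliest) with no requirement to be observed through the 28-day DLT period, so some early leavers count as DLT-free on an unfinished window

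*Protocol*

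**What the plan says.** - **Who is evaluable.** Protocol 14.3 takes "subjects in the Safety Population who received at least 80% of planned study treatment during cycle 1". Protocol 7.5.1 uses the same 80% threshold and adds that a non-evaluable subject is replaced. SAP 6.1.1 keeps it: "participants in the Safety Population who received at least 80% of planned study treatment during cycle 1".
- **The observation window.** Protocol 7.5.1: "DLT period is 28 days of cycle 1 of the dose escalation part". Protocol 14.1: "only those DLTs that occur within the first cycle will be used for safety assessment".
- **Where evaluability is used.** The columns of Table 15 are indexed by "The number of evaluable patients at the current dose". The DLT rate printed under Protocol Figure 4 and SAP Figure 2 also has evaluable patients as its denominator.
- **Planned Cycle 1 dosing in escalation.** The Synopsis says the "patient will not receive Ezm0414 on Cycle 1 Day 2 and on Cycle 1 Day 3". Section 11 has daily dosing from Day 4 to Day 28.
- **Stagger.** Section 7.1 keeps successive subjects at a dose level at least 48 hours apart.
- **Follow-up after leaving.** Under 13.3, AE collection runs to the safety follow-up about 30 days after the last dose, but ends sooner if an investigational or anticancer therapy starts. Under 8.3, data are used up to withdrawal of consent, plus public records where permitted.

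**The concern.** The primary safety endpoint is DLT status over 28 days, but the condition for entering its denominator is an amount of drug. The two coincide only for a subject who stays under observation to Day 28. A subject who meets the dose threshold and is then lost to observation has unknown DLT status, yet the definition counts that subject as evaluable and, with no event recorded, as DLT-free.

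For such a subject a DLT on the unobserved days can only be missed. The observed rate at that dose can therefore be too low, and the escalation boundary of 0.197 is then met somewhat more easily, in a first-in-human trial.

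The efficacy looks show the contrast. The text under Tables 16 and 17 says how mature the response data must be before those boundaries are applied. No comparable statement accompanies Table 15.

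**Working it through.** **1. The plan's own rule.** With target φ = 0.25 and the usual multiples φ1 = 0.6φ = 0.15 and φ2 = 1.4φ = 0.35 (assumed; the documents do not state them):

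- escalation boundary = ln(0.85/0.75) / ln[(0.25×0.85)/(0.15×0.75)] = 0.1252/0.6360 = 0.197
- de-escalation boundary = ln(0.75/0.65) / ln[(0.35×0.75)/(0.25×0.65)] = 0.1431/0.4796 = 0.298

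Both match Protocol 14.1. With the uniform prior and the 0.8 cut-off for elimination, all 27 cells of Table 15 are reproduced. The table is sound; the question is who enters it and when.

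**2. When the 80% threshold is met.** Planned doses: Day 1 plus Days 4-28 = 1 + 25 = 26. 0.8 × 26 = 20.8, so 21 doses are needed. With none missed, the 21st dose falls on Day 23 (Day 1, then 20 doses on Days 4-23). Days 24-28 remain: 5/28 = 18% of the window.

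**3. Who can be counted with those days unobserved.**

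| Subject with at least 21 doses and no DLT so far | Observed to Day 28? |
|---|---|
| Stops drug, stays in the study | Yes, AE collection continues (13.3) |
| Withdraws consent on Days 24-28 | No, data end at withdrawal (8.3) |
| Starts another anticancer therapy on Days 24-28 | No, AE collection ends (13.3) |

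The last two rows are evaluable as the definition stands, whenever the decision is taken.

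**4. Size for one such leaver.** Take a true 28-day DLT rate p = 0.40. The onset pattern is an assumption, so two are used. The probability of no DLT by day d is S(d) = (1−p)^(d/28) under constant hazard, or 1 − p·d/28 under uniform onset.

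- S(23) = 0.657 (constant hazard) or 0.671 (uniform); S(28) = 0.600.
- Chance that this subject has a DLT falling only on Days 24-28: 0.657 − 0.600 = 0.057, or 0.671 − 0.600 = 0.071.
- P(0/3) with one leaver at Day 23: 0.6² × 0.657 = 0.237, or 0.6² × 0.671 = 0.242, against 0.6³ = 0.216.

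**5. Size if Table 15 were applied the day the last subject qualified.** At the minimum 48-hour stagger, when the third subject is at Day 23 the others are at Days 25 and 27. Of six, three are at Days 23, 25 and 27 and the other three have passed Day 28.

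| p = 0.40 | Full window | Constant hazard | Uniform onset |
|---|---|---|---|
| S(27), S(25), S(23) | 0.600 each | 0.611, 0.634, 0.657 | 0.614, 0.643, 0.671 |
| P(0/3) = product | 0.216 | 0.255 | 0.265 |
| P(0/6) | 0.047 | 0.055 | 0.057 |
| P(1 or fewer of 6) | 0.233 | 0.260 | 0.268 |

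For six, P(0/6) is 0.6³ times the product in the row above it, and P(1 or fewer) = P(0/6) × [1 + Σ(1−S)/S]. Under constant hazard: 0.0550 × (1 + 2 + 0.637 + 0.578 + 0.521) = 0.260. Under uniform onset: 0.0573 × (1 + 2 + 0.628 + 0.556 + 0.489) = 0.268.

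**The case against.** **Timing of the decision.** A reader might infer that the plan lets escalation go ahead at Day 23, before DLT status is known. The documents do not support that. Nothing permits a Day 23 decision. The 28-day period, the use of all first-cycle DLTs and the phrase "received at least 80% of planned study treatment during cycle 1" read most naturally as an end-of-cycle judgement, and the Safety Review Committee decides on all available data. The conduct flowchart (Protocol Figure 4, SAP Figure 2) is not shown in the text available and may carry a waiting rule. What stands is that the text shown does not state the wait. Step 5 is therefore conditional on a decision taken immediately.

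**Follow-up.** Stopping drug does not end observation, as step 3 shows. The unobserved group is narrow, and the documents give no frequency for it.

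**Duration-dependent events.** Table 3 excepts "Grade 3 fatigue for less than one week" from the Grade 3 non-haematological DLTs, so one might argue that late fatigue escapes the count. It does not clearly do so: an unresolved event has not met the exception and is a DLT by default. Only the rule for assigning an event to Cycle 1 is left unstated.

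**Final MTD and reporting.** An upward bias in the final MTD is not shown. The MTD comes from isotonic regression, and an observed DLT on Days 24-28 is still a first-cycle DLT that enters it. Nor does the SAP plan a DLT-rate table: after termination during escalation it lists data for three dose levels. SAP 8.4.1 does still base DLT evaluation on this population.

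**Conclusion.** The concern holds as a gap in the definition. Evaluability rests on dose alone, is reachable on Day 23, and takes in subjects without a DLT who withdraw consent or start another anticancer therapy on Days 24-28, with up to 18% of the window unobserved. That follows from the text and needs no assumption about when decisions are made.

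The size is modest. At a true rate of 0.40, one such leaver moves P(0/3) from 0.216 to about 0.24. If decisions were also taken as soon as the last subject qualified, P(0/3) would be 0.255-0.265, and P(1 or fewer of 6) would be 0.260-0.268 against 0.233. These figures rest on the assumed true rate, the two assumed onset patterns and the minimum stagger. If every group is held to Day 28, only the early leavers remain.

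**What to change.** 1. In Protocol 7.5.1 and 14.3 and SAP 6.1.1: a subject without a DLT is evaluable only if he or she received at least 80% of planned Cycle 1 treatment **and** was observed for DLTs through Day 28. Otherwise the subject is replaced under the rule already in 7.5.1.
2. In Protocol 14.1, above Table 15: the table is applied only when every subject in the group has completed the 28-day DLT period, had a DLT, or been declared non-evaluable. If the flowchart already says this, repeat it in the text.
3. State that events are assigned to Cycle 1 by onset date.

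Table 15, its boundaries and the Table 3 criteria stay as they are. The cost is wording, a wait of up to about 5 days per decision if decisions would otherwise be taken as soon as subjects qualify, and an occasional replacement. Because SAP Section 1 reports that the study ended during escalation, the SAP 6.1.1 change is the one that can still affect reporting; the protocol changes matter if the design is used again.
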